**Title: Endoscopic surveillance in patients with serrated polyposis syndrome and low-risk of advanced neoplasia.**

## **STUDY PROTOCOL**

### **SCIENTIFIC BACKGROUND:**

Colorectal cancer (CRC) is the most frequent neoplasm in developed countries considering both sexes and is the second in terms of cancer mortality. The incidence of the CRC is increasing in all developed countries. Detection of precancerous lesions (colon polyps) or malignant lesions (adenocarcinoma) in early stages in screening programs improves the prognosis and decreases the mortality of these patients. Serrated polyposis syndrome (SPS) is the most common colorectal polyposis syndrome and is characterized by the combination of large and/or numerous serrated lesions (SL) throughout the colorectum. There are three different types of SLs described: hyperplastic polyps (HP), sessile serrated lesions (SSL) and traditional serrated adenomas (TSA).

In 2010 the world health organization (WHO) defined the clinical criteria for the SPS diagnosis: criteria I, any patient with  $\geq 5$  serrated lesions proximal to the sigma, two of them  $> 1$  cm in size; criteria II, any first degree relative of a SPS patient with at least one serrated lesion; criteria II, any patient with  $\geq 20$  serrated lesions throughout the colon. This criteria were reviewed in 2019 and criteria II was eliminated. The new criteria are: criteria 1, any patient with  $\geq 5$  SL proximal to the rectum, all  $\geq 5$  mm in size, with at least 2 lesions  $\geq 10$  mm in size; criteria 2, any patient with  $>20$  SL of any size distributed throughout the colon, with  $\geq 5$  lesions proximal to the rectum.

In recent years, a new pathway in the development of colorectal adenocarcinoma have been described, the "serrated pathway". It is associated with mutations in BRAF and KRAS genes, the existence of hypermethylation in the promoter regions "CpG island" and microsatellite instability phenotype caused by methylation of the MLH-1 gene. This new pathway has a faster progression from the serrated polyp to the CRC in comparison with the classic "adenoma-carcinoma" pathway, hence the importance of detecting and removing these lesions in patients with SPS.

CRC prevalence in patients diagnosed with SPS is 15-35%, according to different studies, and the probability at 5 years of developing a CRC is around 1.3-1.9%. During surveillance, the incidence of advanced neoplasia (advanced adenoma or advanced serrated lesions) at 3 years is 13% for adenomas and 42 for serrated lesions. Risk factors for developing CRC and advanced neoplasia have been described in several studies. One of these factors is the SPS criteria 2, which has been demonstrated as a low risk of CRC and advanced neoplasia during surveillance of SPS patients. Detecting more than two sessile serrated lesions proximal to the splenic flexure, one sessile serrated lesion with high grade of dysplasia and the detection of advanced neoplasia in

previous colonoscopies, are all risk factors of developing advanced neoplasia during surveillance. A recent multicentre prospective study established SPS patient surveillance according to lesions detected at last colonoscopy. Individuals with at least one advanced adenoma, an advanced serrated lesion or more than 5 relevant lesions (sessile serrated lesions, adenomas of any size or hyperplastic polyps more than 5 mm) were followed at one year. Patients with no lesions mentioned before were followed at 2 years with colonoscopy. Advanced neoplasia incidence in 2 years recommendation surveillance was 15.6% compared with 24.4% in the 1 year recommendation surveillance. CRC cumulative 5 years incidence was 1.3%. Regarding SPS type, the 5 years advanced neoplasia incidence was lower for patients with SPS criteria III of 2010 (26%) than for patients diagnosed with criteria I (53%) or criteria I and III (59%). In this study patients starting their surveillance with clearing phase achieved (clear colon of all polyps  $\geq$ 5mm and all polyps with the optical aspect of adenoma, TSA or SSL) were at low risk of advanced neoplasia than patients without this phase achieve prior to study inclusion (HR: 0.64; p<0.047).

With all the above described, it can be define a SPS patient with low risk of advanced neoplasia during surveillance: those patients with clearing phase achieved and without any advanced lesion or less than 5 relevant lesions at last colonoscopy.

The Spanish Society of Gastroenterology (AEG) recommends surveillance with colonoscopies in 1-3 years interval for SPS patient, as it does the European Society of Digestive Oncology (ESDO). The European Society of Gastrointestinal Endoscopy (ESGE) recommends surveillance at 1 o 2 years depending on the last colonoscopy findings, annually in case of any advanced adenoma or serrated lesion or  $\geq$ 5 relevant lesions (adenomas, SSL or HP $\geq$ 5mm) were removed, and two surveillance in all other cases. The British Society of Gastroenterology (BSG) recommends annually surveillance for SPS patients until all serrated lesions  $\geq$  are removed, and then 2 year-surveillance. All these Guidelines mention the limited evidence to support their recommendations and the need for prospective studies to evaluate them. As well many authors have expressed the possibility of extending the surveillance to 3 or even 5 years in low risk patients.

The aim of the study is to determine if SPS patients with SPS criteria 1 or 2, with clearing phase achieved and without any advanced lesion or less than 5 relevant lesions at last colonoscopy have the same advanced neoplasia incidence in the surveillance colonoscopy at 2 or 3 years.

## **OBJECTIVES:**

Principal:

- Evaluate the incidence of CCR and advanced neoplasia in SPS patients with low risk factors of advanced neoplasia during surveillance.

Secondary:

- Compare the incidence of advanced neoplasia between patient surveillance with colonoscopy at 2 and 3 years.
- Describe low risk factors of advanced neoplasia in SPS patient in our environment.
- Identify a group of patients with SPS and low risk of advanced neoplasia.

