## **METHODS**

This is a prospective, randomized (1:1) and multicenter study, in Spanish national hospitals, with SPS patients diagnosed according to the reviewed WHO criteria in 2019, in a surveillance program and who meet all the inclusion criteria and no exclusion criteria.

Inclusion criteria:

- Patients aged 18 years or older that fulfil WHO criteria 1 or 2 of SPS.
  - Criteria 1: any patient with  $\geq 5$  SL proximal to the rectum, all  $\geq 5$  mm in size, with at least 2  $\geq 10$  mm in size.
  - Criteria 2: any patient with  $>20$  SL of any size distributed throughout the colon, with  $\geq 5$  lesions proximal to the rectum.
- Patients with a previous complete colonoscopy with adequate bowel preparation and with all lesions  $>5$  mm been resected ("clearance colonoscopy"), after the diagnostic of SPS.
- Nor advanced adenoma or serrated lesions at prior colonoscopy, and also either more than 5 relevant lesion (adenoma, SSL or PH $>5$ mm) at prior colonoscopy.

Exclusion criteria:

- Patients with no informed consent or who do not agree to participate in the study.
- Patients with total or partial colectomy.
- Patients with other CCR predisposing syndromes with germinal mutation (Familial adenomatous polyposis, Lynch syndrome, Peutz-Jehgers syndrome, Cowden syndrome, Juvenile polyposis syndrome...).

- Patients with chronic inflammatory bowel disease.
- Patients with coagulation disorders.
- Fragmented lesion or submucosal invasive lesion at last colonoscopy.
- Inadequate colon preparation: any segment of the colon with <2 points in Boston Scale (BBPS).

Patients selected for the study will be randomised in two groups for the surveillance: group 1, surveillance with colonoscopy in two years; group 2, surveillance with colonoscopy in three years. Randomization will be done at the database program (RedCAP).

All colonoscopies will be performed with high definition (HD) system and it will be the choice of the endoscopist whether to use chromoendoscopy with indigo carmine or virtual chromoendoscopy. Protocol bowel preparation will be recommended by each centre. Sedation will be prescribed and decided by the endoscopist during the examination.

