## SAMPLE SIZE CALCULATION

This is a randomized controlled study for evaluating a non inferiority strategy in the surveillance of SPS patients, between colonoscopy in 2 years and colonoscopy in 3 years, with the incidence of advanced neoplasia as the principal aim of the study. In the study from the Netherlands, Bleijenberg and col., the incidence of advanced neoplasia in patients at 2 years surveillance was of 15%. The investigators assume an acceptable increase of advanced neoplasia at 3 years surveillance of 25%, so the margin for no inferiority is 10% between the two groups. Accepting the type I error with an unilateral contrast of 0.025, beta risk of 0.2 (power 80%) and considering a 10% of lost patients, 69 patients in each group (136 in total) are needed to detect significance differences between the two groups.

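### The objectives make an incidence with no arms principal and the randomised 2- v 3-year comparison secondary, in conflict with the aim, the design and the sample-size section

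*Combined protocol and SAP*

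**What the plan says.** All references are to the combined protocol and SAP.

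- **OBJECTIVES, principal:** "Evaluate the incidence of CCR and advanced neoplasia in SPS patients with low risk factors of advanced neoplasia during surveillance". No arm, contrast or margin is mentioned.
- **OBJECTIVES, secondary, first item:** "Compare the incidence of advanced neoplasia between patient surveillance with colonoscopy at 2 and 3 years".
- **SCIENTIFIC BACKGROUND, closing paragraph:** the aim is to determine whether low-risk patients "have the same advanced neoplasia incidence in the surveillance colonoscopy at 2 or 3 years".
- **METHODS:** "This is a prospective, randomized (1:1) and multicenter study", with the arms given as "group 1, surveillance with colonoscopy in two years; group 2, surveillance with colonoscopy in three years". Advanced neoplasia is defined to include any colorectal cancer (CRC).
- **SAMPLE SIZE CALCULATION:** "This is a randomized controlled study for evaluating a non inferiority strategy in the surveillance of SPS patients", continuing "between colonoscopy in 2 years and colonoscopy in 3 years, with the incidence of advanced neoplasia as the principal aim of the study". It uses 15% at 2 years, up to 25% as acceptable at 3 years, a 10% margin, one-sided type I error 0.025, 80% power and 10% loss, and arrives at 69 per group.
- **STATISTICAL ANALYSIS PLAN:** the two intervals are compared by logistic regression with an odds ratio. This analysis is not called primary, and the margin is not mentioned.

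**The concern.** The protocol gives two competing accounts of its main question. The background, the randomisation and the sample-size section all point to a comparison of intervals. The objectives put that comparison second, behind an incidence that could be estimated without randomising anyone.

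What is at stake is which result the trial will be judged on. A reader could defend either one as primary, and the choice could be made after the data are seen. If the principal objective is followed literally, its result cannot say whether 3 years is acceptable relative to 2. The principal objective also names CRC separately, although the trial will see too few cancers to evaluate it.

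**Working it through.** **1. What was the trial sized for?** Inputs from SAMPLE SIZE CALCULATION: 15%, 25%, margin 0.10, one-sided 0.025, power 80%, 10% loss.

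The two-arm non-inferiority formula is n = (1.960 + 0.842)² × [p₁(1−p₁) + p₂(1−p₂)] / d², with (1.960 + 0.842)² ≈ 7.849.

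- The stated 69 is reproduced with p₁ = 0.15, p₂ = 0.25 and d = 0.20: 7.849 × (0.1275 + 0.1875) / 0.04 = 61.8, so 62 evaluable. Then 62 / 0.9 = 68.9, so 69 per arm.
- A distance of 0.20 is the 10-point margin added to the 10-point difference. That is the direction for a favourable outcome, and advanced neoplasia is harmful.
- None of the other variants tried gives 69: superiority of 15% v 25% needs 250 per arm before loss, and a one-sample test of 25% against 15% needs 114.

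So the sample size comes from a two-arm non-inferiority calculation, for the comparison that the objectives call secondary.

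**2. Can an overall incidence answer the comparison?** At 1:1 the overall rate is (p₂ᵧ + p₃ᵧ) / 2.

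| 2-year | 3-year | Overall | Difference |
|---|---|---|---|
| 15% | 25% | 20% | 10 points, at the margin |
| 20% | 20% | 20% | 0 |

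The same overall figure fits both, so it cannot show or refute non-inferiority.

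**3. How many cancers?** SCIENTIFIC BACKGROUND gives 1.3–1.9% over 5 years. Assume a constant hazard h = −ln(1 − risk) / 5 and 62 evaluable per arm (69 × 0.9). Expected cancers are 62 × (1 − e^(−ht)).

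- At 1.3%, h = 0.00262: 0.32 at 2 years and 0.48 at 3 years.
- At 1.9%, h = 0.00384: 0.47 at 2 years and 0.71 at 3 years.

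That is fewer than one per arm. Zero in 62 would still leave an exact upper 95% limit of 1 − 0.025^(1/62) = 5.8%.

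**4. What power does the comparison have once it is primary?** Power = Φ[(0.10 − true difference) / SE − 1.960], with 62 per arm.

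- Both true rates 15%: SE = √(2 × 0.1275 / 62) = 0.0641. Power = Φ(1.559 − 1.960) = Φ(−0.401) ≈ 34%.
- 15% v 21.6%: the 3-year rate is 1 − 0.85^1.5 = 0.216 under a constant hazard. SE = √[(0.1275 + 0.1693) / 62] = 0.0692. Power = Φ(0.034 / 0.0692 − 1.960) = Φ(−1.47) ≈ 7%.

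For 80% power with both rates at 15%: 7.849 × 0.255 / 0.01 = 200.1, so 201 evaluable, and 201 / 0.9 = 223.3, so 224 randomised per arm.

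**The case against.** The best defence is that the sections complement each other: the objectives name the endpoint, and the sample-size section supplies the contrast. That section does attach the phrase principal aim to advanced neoplasia within the 2 v 3 year design. This would be persuasive if the objectives stopped at the principal item. They go on to list the comparison separately, as secondary, so the conflict stands.

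Other parts of the defence are sound and limit the point. There are three stronger readings that a reader might infer and the documents do not support:

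- *That the plan commits to one pooled, confirmatory incidence.* Neither word appears in the objectives, and no section specifies such a figure. What can be said is that the principal objective names no arms or contrast. A size put on a pooled figure is equally uncertain: it would be 18.3% under a constant hazard (the mean of 15% and 21.6%) and 20% on the protocol's own 15% and 25%.
- *That the type I error and margin belong to no primary objective.* That is so only if the objectives are read alone. The sample-size section ties both to a principal aim. The fault is two competing statements, not a missing one.
- *That the trial cannot address 2 v 3 years.* Randomisation, the outcome definition and a between-arm analysis are in place under either label. What fails is the principal result as worded.

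**Conclusion.** The point holds as an internal inconsistency about which objective is principal. The contradiction and the non-identification in step 2 need nothing beyond the protocol's own text and rates. The cancer counts assume a constant hazard and 62 evaluable patients per arm. The power figures assume 62 evaluable per arm, a normal approximation and the stated true rates, and the 21.6% is itself a constant-hazard assumption because the documents give no expected 3-year rate.

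The inconsistency should be corrected before results are known. It does not invalidate the design, but resolving it in favour of the comparison means that the stated 80% power can no longer be left as it is.

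**What to change.** - **OBJECTIVES.** Make the principal objective whether the incidence of advanced neoplasia with colonoscopy at 3 years is non-inferior to that at 2 years, with a margin of 10 percentage points. CRC need not be named separately, because METHODS already counts it within advanced neoplasia. Move the descriptive incidence to secondary and report it by arm, with CRC as counts by arm and exact confidence intervals.
- **STATISTICAL ANALYSIS PLAN.** Name as primary the risk difference (3-year minus 2-year), and conclude non-inferiority if the upper limit of its two-sided 95% confidence interval is below 10 points. Keep the odds ratio as supportive, since it does not test a percentage-point margin.
- **SAMPLE SIZE CALCULATION.** Restate the power with its assumed true rates: about 34% at 15% v 15% and about 7% at 15% v 21.6%, with about 62 evaluable per arm.

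**Cost.** The changes to the objectives and analysis need wording and a modest analysis specification, with no extra patients or data. The downside is that the plan must then say openly that the present size is unlikely to demonstrate non-inferiority. Restoring 80% power with both rates at 15% would need 224 per arm, and whether to do so is a separate decision.

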## **METHODS**

This is a prospective, randomized (1:1) and multicenter study, in Spanish national hospitals, with SPS patients diagnosed according to the reviewed WHO criteria in 2019, in a surveillance program and who meet all the inclusion criteria and no exclusion criteria.

Inclusion criteria:

- Patients aged 18 years or older that fulfil WHO criteria 1 or 2 of SPS.
  - Criteria 1: any patient with  $\geq 5$  SL proximal to the rectum, all  $\geq 5$  mm in size, with at least 2  $\geq 10$  mm in size.
  - Criteria 2: any patient with  $>20$  SL of any size distributed throughout the colon, with  $\geq 5$  lesions proximal to the rectum.
- Patients with a previous complete colonoscopy with adequate bowel preparation and with all lesions  $>5$  mm been resected ("clearance colonoscopy"), after the diagnostic of SPS.
- Nor advanced adenoma or serrated lesions at prior colonoscopy, and also either more than 5 relevant lesion (adenoma, SSL or PH $>5$ mm) at prior colonoscopy.

Exclusion criteria:

- Patients with no informed consent or who do not agree to participate in the study.
- Patients with total or partial colectomy.
- Patients with other CCR predisposing syndromes with germinal mutation (Familial adenomatous polyposis, Lynch syndrome, Peutz-Jehgers syndrome, Cowden syndrome, Juvenile polyposis syndrome...).

- Patients with chronic inflammatory bowel disease.
- Patients with coagulation disorders.
- Fragmented lesion or submucosal invasive lesion at last colonoscopy.
- Inadequate colon preparation: any segment of the colon with <2 points in Boston Scale (BBPS).

Patients selected for the study will be randomised in two groups for the surveillance: group 1, surveillance with colonoscopy in two years; group 2, surveillance with colonoscopy in three years. Randomization will be done at the database program (RedCAP).

All colonoscopies will be performed with high definition (HD) system and it will be the choice of the endoscopist whether to use chromoendoscopy with indigo carmine or virtual chromoendoscopy. Protocol bowel preparation will be recommended by each centre. Sedation will be prescribed and decided by the endoscopist during the examination.

Data from all the resected and visualized lesions during the colonoscopy will be collected on the database. A pathologist familiarized with serrated lesions will be in charge of the sample analysis. Serrated lesions will be classified according to WHO criteria for serrated lesions. The investigators define “advanced adenoma” as adenomas  $\geq 10$  mm with villous histology and/or with high grade of dysplasia (HGD). We define “advanced SL” as any SL  $\geq 10$  mm and any SL with dysplasia. The investigators define “advanced neoplasia” as any CRC, any advanced adenoma or advanced SL.

Quality of bowel cleansing will be graded by each endoscopist following the Boston Bowel Preparation Scale. This scale evaluates each segment (ascending colon, transverse colon and descending colon) of the following form: 0 = segment of colon whose mucosa cannot be seen due to the existence of solid stools that cannot be eliminated; 1 = mucosa portion of a colonic segment that can be seen, but other areas of the colonic segment are not seen, either due to the presence of dirt, feces or opaque liquid; 2 = existence of small amount of dirt, small fragments of stool and / or opaque liquid, but the mucosa of the colonic segment can be seen well; 3 = all the mucosa of the colonic segment can be seen well without residual dirt, small traces of stool or opaque liquid. Patients with inadequate preparation (when in any segment the score is 0 or 1, or the total score is less than 6) will be excluded from the study.

During colonoscopy all complications as post-polypectomy bleeding, perforation or cardio-respiratory events will be registered. Those complications will be considered if surgery or hospital admission is required.

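### The inclusion criterion admits patients with exactly 5 relevant lesions, while the low-risk definition and the aim require fewer than 5

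*Combined protocol and SAP*

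**What the plan says.** All references are to the combined protocol and SAP.

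- **Low-risk definition (Scientific Background).** Low-risk patients are "those patients with clearing phase achieved and without any advanced lesion or less than 5 relevant lesions at last colonoscopy". The aim, at the end of the same section, repeats the cut-off of fewer than 5.
- **Inclusion criteria (Methods).** After ruling out advanced adenomas and advanced serrated lesions at the prior colonoscopy, the criterion continues "and also either more than 5 relevant lesion". Relevant lesions are adenomas, SSLs and hyperplastic polyps above 5 mm.
- **Source study (Scientific Background).** An advanced lesion led to a 1-year interval. So did the lesion count, for which the text reads: "more than 5 relevant lesions (sessile serrated lesions, adenomas of any size or hyperplastic polyps more than 5 mm) were followed at one year". All others returned at 2 years. The rates are given as follows: "Advanced neoplasia incidence in 2 years recommendation surveillance was 15.6% compared with 24.4% in the 1 year recommendation surveillance".
- **Guidelines (Scientific Background).** ESGE, as summarised, recommends colonoscopy "annually in case of any advanced adenoma or serrated lesion or" 5 or more relevant lesions. The Spanish society "recommends surveillance with colonoscopies in 1-3 years interval for SPS patient, as it does the European Society of Digestive Oncology (ESDO").
- **Sample Size Calculation.** 15% advanced neoplasia at 2 years, a 10-point non-inferiority margin, 10% loss and 69 patients per group.

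**The concern.** The trial is meant to say whether a defined low-risk group can wait 3 years instead of 2. The definition and the aim cover 0 to 4 relevant lesions; the criterion that sites will apply covers 0 to 5. No other section reconciles them.

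Two things are at stake. First, applicability: one secondary objective is to identify a low-risk group, and readers could not tell whether a patient with exactly 5 lesions belongs to it. Second, a limited safety point: under the ESGE rule as summarised such a patient would return after 1 year, while this trial may assign 3. That may be acceptable, but it should be a stated choice. Loose wording in a multicentre trial also leaves room for centres to apply the cut-off differently.

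**Working it through.** The plan gives no figure to reproduce on this point. The check is a comparison of texts, followed by an illustration of size.

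**1. Reading the wording.** Neither sentence is clean. The definition joins its conditions with *or*; taken literally, an advanced lesion would be allowed if the count were low, which cannot be meant in a low-risk definition. The inclusion criterion opens with a negative and then uses *either*; the only sensible reading is that neither advanced lesions nor more than 5 relevant lesions are allowed. After these repairs, both numbers are legible.

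**2. Where exactly 5 falls.**

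| Place | Rule | Patient with exactly 5 |
|---|---|---|
| Low-risk definition | fewer than 5 | outside |
| Aim | fewer than 5 | outside |
| Inclusion criterion | not more than 5 | eligible |
| Source study, as described | more than 5 goes to 1 year | 2-year group |
| ESGE, as summarised | 5 or more goes to annual | annual |

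The definition and the criterion differ at this single value.

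**3. Number affected.** The documents do not give the share *f* with exactly 5, so *f* = 5%, 10% and 20% are assumptions. The 69 per arm is taken as stated; whether it is adequate is a separate question.

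- Affected per arm: 69 × f = 3.5, 6.9, 13.8.
- Evaluable per arm after 10% loss: 69 × 0.9 = 62.1.
- Left in a sensitivity analysis without them: 62.1 × (1 − f) = 59.0, 55.9, 49.7.

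**4. Effect on the expected rate.** On the protocol's account, the source study's 2-year group already includes patients with exactly 5, so the expected change is nil. As an unfavourable illustration, give them the 1-year group's rate, although it was measured at 1 year:

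- Rate = 15.6 + f × (24.4 − 15.6) = 15.6 + 8.8f
- f = 5%: 16.04% (shift 0.44 points)
- f = 10%: 16.48% (shift 0.88 points)
- f = 20%: 17.36% (shift 1.76 points)

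Each shift is small against the 10-point margin.

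**The case against.** The strongest reply is that the criterion follows the source study. The Background describes that study's cut-off as more than 5, with hyperplastic polyps counted above 5 mm, and the inclusion criterion matches on both. The 15% planning rate appears to come from the same study, so the enrolled population fits the planning assumption. This stands. It means that the definition and the aim may be the texts to correct, and the fix allows for that. It does not remove the mismatch.

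A second reply is that this is a drafting slip with little effect. A slip is plausible and the effect is probably small. But the slip lies between the operative eligibility rule and the trial's own question, so it is worth correcting.

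A reader might also infer three stronger points that the documents do not support:

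- **That the hyperplastic polyp threshold is wrong.** Only the ESGE rule counts these polyps from 5 mm, and the protocol does not say that it adopts ESGE. The trial's threshold of more than 5 mm agrees with its account of the source study.
- **That the clearance criterion contradicts the protocol.** Methods requires lesions above 5 mm to be resected. The stricter version, from 5 mm "and all polyps with the optical aspect of adenoma, TSA or SSL", belongs to the cited study: the sentence begins "In this study patients starting their surveillance with clearing phase achieved". Methods gives the trial's own working definition. All that is open is which version the aim's clearing phase refers to. The hazard ratio of 0.64 compares patients cleared with patients not cleared before inclusion, so it does not measure this difference in wording.
- **That patients with exactly 5 lesions are put at clear risk.** Both trial intervals lie within the 1 to 3 years that AEG and ESDO allow, as summarised. The BSG rule moves to 2 years after clearance, but its size threshold is missing from the text, so it cannot settle the matter.

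**Conclusion.** The mismatch is certain on the text: patients with exactly 5 relevant lesions are eligible but outside the stated target population. It should be corrected; it does not threaten the validity of the trial.

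- **Bias.** A reader might infer a biased comparison. Randomisation places these patients in both arms, so their inclusion does not favour either. If a third year were worse for them in particular, that would be a real effect in the enrolled population; the documents give no 3-year rate to judge it.
- **Planning rate.** A reader might infer that 15% is too low. The protocol's account places these patients in the 2-year group, so the rate is not undermined. This rests on that account being accurate, which cannot be checked from the documents.
- **Size.** About 3 to 14 patients per arm, and at most 0.4 to 1.8 points on the expected rate in the unfavourable illustration. Both rest on an assumed share of 5% to 20%.

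**What to change.** Use one cut-off throughout. The documents do not show whether enrolment has begun, so there are two routes.

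- **Before enrolment.** Change the inclusion criterion and the REDCap eligibility check to: *no advanced adenoma or advanced serrated lesion, and fewer than 5 relevant lesions (adenoma, SSL, or hyperplastic polyp >5 mm), at the prior colonoscopy.* Cost: one line, a few boundary patients become ineligible, and the cut-off is slightly stricter than the source study's as described.
- **If patients with exactly 5 are already enrolled, or the source study's cut-off is intended.** Restate the definition and the aim as *5 or fewer*, leave eligibility unchanged, and report a sensitivity analysis without patients who have exactly 5. Cost: one line each in the definition and the aim, and one further analysis on about 50 to 59 patients per arm under the assumed shares.

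On either route, leave the hyperplastic polyp threshold at more than 5 mm. For clearance, add at most one line saying which definition the aim's clearing phase means. Change that criterion only if the cited study's version is intended and enrolment has not started: it applies to a colonoscopy already done, so it could exclude more patients or require checking of endoscopy reports.
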